## 4. STUDY DESIGN

### 4.1. Overall Design

Study 207966 (Antiretroviral Therapy as Long Acting Suppression every 2 Months-ATLAS-2M) is a Phase III, randomized, open-label, active-controlled, multicenter, parallel-group, non-inferiority study designed to assess the antiviral activity and safety of CAB LA + RPV LA administered every 4 weeks compared CAB LA + RPV LA administered every 8 weeks in approximately 1020 adult HIV-1 infected patients.

Two groups of patients who fulfill eligibility requirements will be randomized (1:1) at Day 1 to receive CAB LA + RPV LA Q4W, or CAB LA + RPV LA Q8W regimen for at least 100 weeks:

#### Group 1: Patients randomized from current ART Standard of Care (SOC) therapy

Patients randomized from current ART SOC therapy, including those enrolled to the “current ART” arm of the ATLAS study following completion of the Week 52 visit (at

minimum), will begin oral therapy with CAB 30 mg + RPV 25 mg once daily at Day 1 for 28 days ( $\pm 3$  days) to determine individual safety and tolerability prior to receiving CAB LA + RPV LA Q4W, or CAB LA + RPV LA Q8W. For patients on SOC transitioning from the ATLAS trial, eligibility for ATLAS-2M can be determined once the final central lab results from ATLAS are available and safety parameters have been reviewed.

Group 2: Patients currently receiving CAB LA + RPV LA Q4W

At Day 1, patients entering ATLAS-2M from ATLAS and currently receiving CAB LA + RPV LA Q4W (including both those who were originally randomized to Q4W in the Maintenance phase of ATLAS and those who transitioned from SOC to the Q4W regimen within the Extension Phase of ATLAS) will be randomized 1:1 to either continue Q4W administration or transition to Q8W administration of CAB LA + RPV LA. The first injection visit for ATLAS-2M can be performed once the final central lab results from ATLAS are available and safety parameters have been reviewed, and the ATLAS Week 52 visit (at minimum) has been completed. Participants will continue to receive CAB LA + RPV LA Q4W injections as scheduled within the ATLAS trial until their eligibility for ATLAS-2M can be fully evaluated and the participant is re-randomized (Q4W or Q8W). If determined to be ineligible for ATLAS-2M, those participants can elect to continue participation in ATLAS or withdraw from the ATLAS study.

Participants in ATLAS-2M who successfully complete Week 100 (without meeting study defined withdrawal criteria) will be given the option to continue to receive their randomized treatment (CAB LA + RPV LA administered Q4W or Q8W) in the Extension Phase through Week 152 and until the study treatment is either locally approved and commercially available within the local sector (including through local public/government health sectors), the participant no longer derives clinical benefit, the participant meets a protocol-defined reason for discontinuation or until development of either CAB LA + RPV LA Q4W and/or Q8W is terminated. Alternatively, participants can choose to complete study participation and enter the 52-week LTFU Phase of the study.

[figure not shown]
Any participant who receives at least one dose of CAB LA and/or RPV LA and discontinues the CAB LA + RPV LA regimen for any reason will enter a 52-week LTFU Phase. Those participants must remain on suppressive highly active antiretroviral therapy (HAART) for at least 52 weeks after the last dose of CAB LA and/or RPV LA.

In order to achieve balance across the treatment arms, randomization will be stratified by prior CAB + RPV Exposure: 0 weeks, 1-24 weeks, >24 weeks. The primary endpoint for the study is the proportion of participants with HIV-RNA greater than or equal to 50 c/mL (Virologic Failure) at Week 48 as per Food and Drug Administration (FDA) Snapshot algorithm using the Intent-to-Treat Exposed (ITT-E) population. The proportion of participants with plasma HIV-1 RNA <50 c/mL at Week 48 using the FDA Snapshot algorithm (Missing, Switch or Discontinuation = Failure, ITT-E population) is a key secondary endpoint comparison.

The sample size of 1020 provides 85% power to demonstrate non-inferiority in the primary endpoint at Week 48 using a 4% margin, assuming a true 3% failure rate for Q8W CAB LA + RPV LA and a 2% failure rate for the Q4W CAB LA + RPV LA arm and a 2.5% one-sided alpha level.

**Figure 1 207966 (ATLAS-2M) Study Design Schematic**

N=1020, randomized 1:1 to each arm and stratified by prior CAB + RPV Exposure  
 # SOC Patients not transitioning from the ATLAS study must be on uninterrupted current regimen (either the initial or second cART regimen) for at least 6 months prior to Screening. Documented evidence of at least two plasma HIV-1 RNA measurements <50 c/mL in the 12 months prior to Screening: one within the 6 to 12 month window, and one within 6 months prior to Screening. No history of virologic failure. No evidence of viral resistance based on the presence of any resistance-associated major INI, or NNRTI mutation (except K103N) from prior genotype assay results. No current or prior history of etravirine use.  
 †Optional Extension Phase to continue randomized CAB LA + RPV LA Q4W or Q8W at Wk 100  
 ‡Participants who withdraw from IM regimen must go into 52 week long term follow up phase if randomized regimen is not yet locally approved and commercially available.

**4.2. Treatment Groups and Duration**

**4.2.1. Screening Phase (Up to 35 days)**

Informed consent must be obtained prior to any study procedures, including any Screening assessment.

Participants will be involved in a Screening period of up to 35 days and may be re-screened once. Participants who are randomized into the trial and subsequently withdrawn from the study, for any reason, may not be re-screened. Participants may be randomized as soon as all eligibility requirements have been confirmed at the site.

For participants transitioning from the ATLAS study, eligibility to transition to ATLAS-2M at Week 52 (at the earliest) will be determined once the final central lab results from ATLAS, following (at minimum) completion of the ATLAS Week 48 visit are available

and safety parameters have been reviewed. Separate Screening Labs will be utilized to inform eligibility for ATLAS-2M; however, in some occasions and upon consultation with the Medical Monitor, individual lab results and safety data from the final visit of the ATLAS study can be considered towards informing eligibility for the ATLAS-2M study as long as all other Screening and eligibility criteria are met.

#### 4.2.2. Maintenance Phase (Day 1 up to Week 100)

[figure not shown]
There are two ways in which study participants may transition to the LA regimen, either directly from oral SOC or from Q4W dosing from ATLAS.

Table 1 and Figure 2 describe the CAB LA + RPV LA dosing regimens in ATLAS-2M based on the mode of transition.

**Table 1 CAB LA + RPV LA Dosing Regimens in ATLAS-2M**

Participants Transitioning from Oral Standard of Care (SOC)		
Regimen	CAB LA	RPV LA
Q4W	CAB LA: Week 4b: 600 mg (Loading Dose) Week 8 & Q4W thereafter: 400 mg	RPV LA: Week 4b: 900 mg (Loading Dose) Week 8 & Q4W thereafter: 600 mg
Q8W	CAB LA: Week 4b, Week 8, & Q8W thereafter: 600 mg	RPV LA: Week 4b, Week 8, & Q8W thereafter: 900 mg
Participants Transitioning from ATLAS Q4W		
Regimen	CAB LA	RPV LA
Q4W	CAB LA: Day 1 & Q4W thereafter: 400 mg	RPV LA: Day 1 & Q4W thereafter: 600 mg
Q8W	CAB LA: Day 1 & Q8W thereafter: 600 mg	RPV LA: Day 1 & Q8W thereafter: 900 mg
All participants entering ATLAS-2M from an oral SOC regimen will receive a 4-week oral lead-in of CAB+RPV prior to receiving IM injections, except for ATLAS subjects transitioning from Q4W to Q8W injections. These participants previously established safety and tolerability of CAB + RPV within the ATLAS study.		

**Figure 2** ATLAS-2M Treatment Schematic

**4.2.2.1. Patients randomized to LA dosing from current ART SOC therapy:**

All participants randomized from current ART SOC therapy (including those transitioning from SOC in ATLAS and new study participants) will begin oral therapy with CAB 30 mg + RPV 25 mg once daily at Day 1 for 4 weeks to determine individual safety and tolerability prior to administration of CAB LA + RPV LA. The oral lead-in period is part of the Maintenance Phase and will therefore be included within the planned analyses.

The final dosing of current daily oral ART regimen should occur the day prior to randomization to avoid overlap of treatment regimens however, if the participant takes current ART prior to coming into the clinic, randomization and initiation of oral CAB and RPV should continue as planned for Day 1. At the Week 4a visit, safety assessments (including e.g., clinical chemistries) will be performed as per the Time and Events Table to determine individual safety and tolerability prior to the initial administration of CAB LA + RPV LA. Dosing of CAB LA + RPV LA Q4W or Q8W will initiate at the Week 4b visit once safety labs from Week 4a are available and have been reviewed.

Subjects receiving oral SOC treatment and randomized to Q4W injections will receive loading doses of CAB LA 600 mg + RPV LA 900 mg on **Week 4b** followed by maintenance injections of CAB LA 400 mg + RPV LA 600 mg every 4 weeks thereafter.

Subjects receiving oral SOC treatment and randomized to Q8W injections will receive doses of CAB LA 600 mg + RPV LA 900 mg on **Week 4b and Week 8** followed by identical maintenance dose injections every 8 weeks thereafter.

All injections should be planned as single injections per drug.

**4.2.2.1.1. IM injections every 4 weeks (Q4W from SOC):**

Week 4b visit only - CAB LA 600 mg + RPV LA 900 mg, each given as 1 X 3 mL IM injection

Week 8 visit and Q4W thereafter - CAB LA 400 mg IM + RPV LA 600 mg IM every 4 weeks for 100 weeks, each given as 1 X 2 mL IM injection

At Week 4b, participants will return to the clinic, take the last oral dose (CAB 30 mg + RPV 25 mg), and receive the first CAB LA (600 mg) + RPV LA (900 mg) injections (within 2 hours of the final oral dose of CAB + RPV). The first injections with IM CAB LA + RPV LA at Week 4b can be performed once central lab results are available and safety parameters are reviewed from the Week 4a visit.

The second and third IM injections with CAB LA 400 mg and RPV LA 600 mg will be performed at Week 8 and Week 12. There will be a -7-day dosing window for the second and third IM injections such that the second injection occurs within the window of Week 7 and Week 8 but no later than Week 8 and the third injection occurs within the window of Week 11 and Week 12 but no later than Week 12. Subsequent injections with CAB LA 400 mg and RPV LA 600 mg will occur every 4 weeks ( $\pm 7$  days) thereafter. In addition, starting after the Week 16 injection, the interval between injection visits will be limited to a maximum of 5 weeks. The Medical Monitor must be contacted to discuss individual participant case management if the length of time between injections exceeds or is projected to exceed 5 weeks.

**4.2.2.1.2. IM injections every 8 weeks (Q8W from SOC):**

Week 4b visit – CAB LA 600 mg + RPV LA 900 mg IM, each given as 1 X 3 mL IM injection

Week 8 visit- CAB LA 600 mg + RPV LA 900 mg IM, each given as 1 X 3 mL IM injection

Week 16 visit and Q8W thereafter - CAB LA 600 mg + RPV LA 900 mg IM, every 8 weeks for 100 weeks, each given as 1 X 3 mL IM injection

At the Week 4b visit, subjects will return to the clinic, take their last oral dose (CAB 30 mg + RPV 25 mg), and receive the first CAB LA (600 mg) + RPV LA (900 mg) injections (within 2 hours of the final oral dose of CAB + RPV). The first injections with IM CAB LA + RPV LA at Week 4b can be performed once central lab results are available and safety parameters are reviewed from the Week 4a visit.

The second loading injection will be administered at Week 8 (CAB LA 600 mg + RPV LA 900 mg, with subsequent injections (CAB LA 600 mg + RPV LA 900 mg) occurring every 8 weeks thereafter. There will be a -7-day dosing window for the second and third IM injections such that the second injection occurs within the window of Week 7 and Week 8 but no later than Week 8 and third injection occurs within the window of Week 15 and Week 16 but no later than Week 16. Subsequent injections with CAB LA 600 mg and RPV LA 900 mg will occur every 8 weeks ( $\pm 7$  days). Starting after the Week 16

injection, the interval between injection visits will be limited to a maximum of 9 weeks. If the length of time between injections exceeds, or is projected to exceed 9 weeks, the Medical Monitor must be contacted to discuss individual participant case management.

#### **4.2.2.2. Participants transitioning from ATLAS and currently receiving CAB LA + RPV LA Q4W**

Subjects receiving Q4W injections within ATLAS and randomized to receive Q4W injections in Study 207966 will continue receiving maintenance injections Q4W as scheduled and will not require a loading dose on Day 1.

Subjects receiving Q4W injections within ATLAS and randomized to receive Q8W injections in Study 207966 will receive doses of CAB LA 600 mg + RPV LA 900 mg on Day 1, one month after their last Q4W maintenance dose, in order to align with Day 1 of study randomization. Subjects will not require an intermediate dose at Week 4 and will receive their next Q8W maintenance injections at Week 8 and Q8W thereafter.

Participants transitioning from the ATLAS study and on CAB LA + RPV LA Q4W treatment will be randomized at Day 1 to either continue Q4W administration or transition to Q8W administration of CAB LA + RPV LA. The first injection visit for the ATLAS-2M study can be performed once the final central lab results from the ATLAS study are available and safety parameters have been reviewed. Screening labs determining eligibility for ATLAS-2M can be collected at Week 48 (at minimum) for participants originally randomized to the Q4W arm within ATLAS. Screening labs for participants who transitioned from SOC to Q4W injections within the ATLAS Extension Phase may be obtained at ATLAS Week 56b (following the CAB + RPV Oral lead-in period) or at subsequent ATLAS visits after receiving one set or a short course of Q4W injections. The transition from the final ATLAS to ATLAS-2M Day 1 dosing must occur 4 weeks ( $\pm 7$  days) from the final injections received in ATLAS

Dosing for participants transitioning from CAB LA + RPV LA Q4W in ATLAS is as follows:

##### **4.2.2.2.1. IM injections every 4 weeks (Q4W from ATLAS Q4W):**

Starting at Day 1, all injections will continue with maintenance doses of CAB LA 400 mg and RPV LA 600 mg administered every 4 weeks ( $\pm 7$  days). In addition, the time between injection visits will be limited to a maximum of 5 weeks. The Medical Monitor must be contacted if the length of time between injections exceeds or is projected to exceed 5 weeks.

##### **4.2.2.2.2. IM injections every 8 weeks (Q8W from ATLAS Q4W):**

Participants transitioning from ATLAS and randomized to receive CAB LA + RPV LA Q8W injections will initiate Q8W dosing at the Day 1 visit as follows:

Day 1- CAB LA 600 mg + RPV LA 900 mg IM, each given as 1 X 3 mL IM injection

Week 8 and Q8W thereafter- CAB LA 600 mg + RPV LA 900 mg IM, each given as 1 X 3 mL IM injection

The second loading injection will be administered at Week 8 (CAB LA 600 mg + RPV LA 900 mg), with subsequent injections (CAB LA 600 mg + RPV LA 900 mg) occurring every 8 weeks thereafter. There will be a -7-day dosing window for the second and third IM injections such that the second injection occurs within the window of Week 7 and Week 8 but no later than Week 8 and third injection occurs within the window of Week 15 and Week 16 but no later than Week 16. Subsequent injections with CAB LA 600 mg and RPV LA 900 mg will occur every 8 weeks ( $\pm 7$  days). Starting after the Week 16 injections, the interval between injection visits will be limited to a maximum of 9 weeks. If the length of time between injections exceeds, or is projected to exceed 9 weeks, the Medical Monitor must be contacted to discuss individual participant case management.

The primary study analysis will consist of data collected through the Week 48 visit. A single repeat of HIV-1 RNA for any participant with a HIV-1 RNA  $\geq 50$  c/mL at Week 48, Week 96, or Week 152 must be performed. The retest should be scheduled as soon as possible (but no later than 4 weeks from the Week 48, 96 or 152 visits, respectively) and will inform the Week 48, 96, or 152 virological endpoint, respectively.

#### **4.2.3. Extension Phase**

Participants who successfully complete 96 Weeks of CAB LA + RPV LA treatment in the Maintenance Phase will continue to have access to their randomized treatment Q4W or Q8W CAB LA + RPV LA in the Extension Phase through Week 152 and until study treatment is either locally approved and commercially available within the local sector (including through local public/government health sectors), the participant no longer derives clinical benefit, the participant meets a protocol-defined reason for discontinuation or until development of either CAB LA + RPV LA Q4W and/or Q8W is terminated. For participants randomized to Q4W arm, dosing visits will continue to occur every 4 weeks with CAB LA 400 mg and RPV LA 600 mg. For participants randomized to the Q8W arm, dosing visits will continue to occur every 8 weeks with CAB LA 600 mg and RPV LA 900 mg. Safety and efficacy assessments will be conducted as per the Time and Events Schedule.

Participants choosing to not enter the Extension phase can complete their study participation at the Week 100 visit and enter into the LTFU Phase as required.

Participants who choose to continue on to the Extension Phase will need to be assessed for eligibility and will continue on their current CAB LA + RPV LA regimen while eligibility is being confirmed. A single repeat of HIV-1 RNA for any participant with a HIV-1 RNA  $\geq 50$  c/mL and  $< 400$  c/mL at Week 96, or Week 152 must be performed. The retest should be scheduled as soon as possible (but no later than 4 weeks from the Week 96 or Week 152 visit). Participants with HIV-1 RNA  $< 50$  c/mL upon retest are eligible to enter the Extension Phase. Participants with HIV-1 RNA  $\geq 400$  c/mL at Week 96 are not eligible to enter the Extension Phase, will not be allowed a repeat to determine eligibility, and will therefore be withdrawn from the study. Eligibility to enter the Extension Phase for any participants with a retest HIV-1 RNA  $> 50$  c/mL and  $< 400$  c/mL will require approval by the study Medical Monitor.

Participants not eligible to enter the Extension Phase or choosing not to participate in the Extension Phase will end their study treatment and enter the LTFU Phase. Sites may be reimbursed for up to a one-month supply of antiretroviral medication to facilitate transition to non-study ART for participants that do not qualify for the Extension Phase.

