**Participants must be discontinued from study treatment for any of the following reasons:**

- Participants who are not eligible to continue into the Maintenance Phase.
- Participants who are not eligible, or do not wish to continue on to the Extension Phase.
- Virologic withdrawal criteria as specified in Section 5.5.4 are met;
- Participant requires substitution of ART;
- Participant requires substitution or dose reduction of CAB LA or RPV LA (oral bridging supply and potential for a second loading dose may be permissible following discussion with the Medical Monitor).
- Liver toxicity where stopping criteria are met and no compelling alternate cause is identified (see Section 5.5.1);
- Renal toxicity are met and no compelling alternate cause is identified;
- QT interval (QTc) interval >550 msec from three or more tracings separated by at least 5 minutes and considered causally related to IP.
- Grade 4 clinical AE considered causally related to study drug;
- Participant has a Grade 3 or higher rash or Grade 2 rash with evidence of systemic involvement and no compelling alternative cause is identified
- Participant withdrew consent

Efficacy data for participants withdrawing from the study will be considered evaluable up to the point at which they are withdrawn using the same criteria for evaluability as for participants who complete the study.

Safety data for all participants who receive any amount of study drug, including participants who withdraw from the study, will be included in evaluations of safety.

All data from the Withdrawal visit will be recorded, as they comprise an essential evaluation that should be done prior to discharging any participant from the study.

The following actions must be taken in relation to a participant who fails to attend the clinic for a required study visit:

- a. The site must attempt to contact the participant and re-schedule the missed visit as soon as possible.
- b. The site must counsel the participant on the importance of maintaining the assigned visit schedule and ascertain whether or not the participant wishes to and/or should continue in the study.

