### **5.5.4. Definition of Protocol-Defined Confirmed Virologic Failure**

For the purposes of clinical management in this study, CVF is defined as:

Rebound as indicated by two consecutive plasma HIV-1 RNA levels  $\geq 200$  c/mL after prior suppression to  $< 200$  c/mL.

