#### **5.5.5.2. Suspected Virologic Failure**

Upon notification that a participant's HIV-1 RNA plasma level meets the definition of virologic failure, the Investigator should confirm the definition is met by initiating a repeat of the HIV-1 RNA assessment.

The following guidelines should be followed for scheduling confirmatory HIV-1 RNA testing in an effort to avoid false-positive results:

- Confirmatory testing should be scheduled within 2 to 4 weeks following resolution of any intercurrent illness, during which time the participant should receive full dose of all IP.
- Confirmatory testing should be scheduled at least 4 weeks following any immunization, during which time the participant should receive full dose of all IP.
- If therapy is interrupted\* due to toxicity management, non-compliance, or other reasons, confirmatory testing should be scheduled 2 to 4 weeks following resumption of full dose of all IP.
- The participant should have received full dose of IP for at least 2 weeks at the time confirmatory plasma HIV-1 RNA testing is done.

\*Note: treatment interruption guidelines above may not apply for participants on CAB LA + RPV LA treatment. The study team should be contacted to discuss any treatment interruptions for participants meeting the definition of virologic failure.

In addition, the Investigator should query the participant regarding intercurrent illness, recent immunization, or interruption of therapy.

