## 6.2. Treatment Assignment

Informed consent must be obtained prior to any study procedures, including Screening visit activities. Participants will be assigned to study treatment in accordance with the randomization schedule. The randomization schedule, including stratification, will be generated using the GSK validated randomization software RANDALL NG. The randomization schedule is comprised of a series of blocks, with equal treatment allocation within each block, which are shared across centers via central randomization. Given the open-label study design, central randomization was used to eliminate selection bias due to foreknowledge of randomized treatment. With central randomization, knowledge at a site of the randomized treatment group for previous subjects does not predict which treatment group will be assigned to the next randomized subject.

Randomization and study treatment assignment will be facilitated by the interactive response technology (IRT) through the central Randomization and Medication Ordering System Next Generation (RAMOS NG).

Following confirmation of fulfillment of study entry criteria, study site personnel will be required to register participants using RAMOS NG for assignment of a unique identifier (designating the participant's randomization code and treatment sequence assignment) for each participant participating in the study. A unique treatment number will be assigned for each participant participating in the study. Participants will be randomized in a 1:1 ratio to CAB LA + RPV LA Q4W or to CAB LA + RPV LA Q8W in accordance with the computer generated randomization schedule.

Participants who successfully complete 100 weeks of treatment and have a viral load <50 c/ml at Week 96 (or upon retest by Week 100) will be given the opportunity to enter the Extension Phase in which they will continue to receive their CAB LA + RPV LA regimen. In addition, RAMOS NG will facilitate the initial supply and subsequent resupply of IP to study sites.

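### After confirmed virologic failure, Section 5.5.5.3 lets study drug continue until resistance results arrive and does not exclude a further long-acting injection

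*Protocol*

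**What the plan says.** **After CVF.** Section 5.5.4 defines CVF as "Rebound as indicated by two consecutive plasma HIV-1 RNA levels" at or above 200 c/mL after earlier suppression below 200. Section 5.5 lists "Virologic withdrawal criteria as specified in Section 5.5.4 are met" among the reasons that oblige discontinuation, and 5.5.5.3 repeats that CVF ends study treatment. The same section then gives the investigator discretion to continue study drug until the resistance results are in, at which time the participant must stop. Treatment must also stop if no genotype or phenotype can be produced. Section 6.1 names CAB LA and RPV LA, with the oral forms, as the investigational study drugs. The risk-of-treatment-failure entry in 2.3.1 says CVF participants come off study drugs and transfer to oral HAART; it mentions no interval.

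**HAART deadline.** Section 4.2.4 sets HAART initiation at 4 weeks (± 7 days) after the last Q4W injection, or 8 weeks (± 7 days) after the last Q8W injection.

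**Extension entry.** Section 4.2.3 (repeated in 1.4.3) requires "A single repeat of HIV-1 RNA for any participant with a HIV-1 RNA" of at least 50 and below 400 c/mL at Week 96. It continues: "Eligibility to enter the Extension Phase for any participants with a retest HIV-1 RNA" above 50 and below 400 c/mL needs Medical Monitor approval. Section 6.2 offers the Extension to participants who complete 100 weeks and "have a viral load <50 c/ml at Week 96 (or upon retest by Week 100"; it does not mention approval.

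**The concern.** Deferring the stop until resistance results arrive is easy to accept for a daily tablet, which can be withdrawn the next day. Here a single dose covers 4 or 8 weeks and cannot be taken back, and 2.3.1 warns that residual CAB may persist for more than a year in some participants. A site that follows 5.5.5.3 as written may give another full dose of a regimen already confirmed as failing. Because 4.2.4 counts from the last injection, that dose also resets the clock for starting HAART. Another site, reading the opening sentence of 5.5.5.3 or the table in 2.3.1, would stop at once.

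The Extension text adds a smaller problem of the same kind. Its approval band runs to 400 c/mL, while the failure rules work at 200 c/mL, and the numeric rule does not refer to them.

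**Working it through.** **1. Effect of one further injection on the HAART deadline.** Inputs: the 4.2.4 windows, and on-schedule dosing at 4 or 8 weeks. Set t = 0 at the last injection before CVF is confirmed.

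- Latest HAART start with no further injection = interval + 1 week. Q4W: 4 + 1 = 5 weeks. Q8W: 8 + 1 = 9 weeks.
- Latest HAART start with one further injection at the next due date = interval + (interval + 1). Q4W: 4 + 5 = 9 weeks. Q8W: 8 + 9 = 17 weeks.
- Shift: 9 − 5 = 4 weeks (Q4W); 17 − 9 = 8 weeks (Q8W).

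The shift does not depend on the 7-day allowance. With the plain 4- and 8-week limits in 2.3.1, the figures are 4 + 4 = 8 against 4, and 8 + 8 = 16 against 8, again a shift of 4 and 8 weeks.

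**2. When the shift occurs.** Let d be the weeks from CVF confirmation to the next due injection, and T the weeks from confirmation to resistance results. The protocol text at hand gives no value for T, so it has to be treated as a range:

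- T no longer than d: results are back, treatment stops, and the shift is 0.
- T longer than d but no longer than d plus one interval: one injection may be given, and the shift is 4 or 8 weeks.
- T longer still: 5.5.5.3 sets no calendar limit, so the permission would cover another dose as well.

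**3. Extension band against the CVF definition.** Split the Week 96 value and the retest at 200 c/mL, assuming earlier suppression below 200:

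| Week 96 value (c/mL) | Retest (c/mL) | Status under 5.5.4 and 5.5.5.2 |
|---|---|---|
| 50–199 | 51–199 | No value at failure level; approval route works as intended |
| 200–399 | 51–199 | Suspected failure, not confirmed by the retest |
| 50–199 | 200–399 | First value at failure level; needs confirmation |
| 200–399 | 200–399 | CVF; mandatory stop |

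All four combinations fall inside the numeric approval band. In the fourth, the stop prevails through general wording. Section 4.2.3 ends access once "the participant no longer derives clinical benefit, the participant meets a protocol-defined reason for discontinuation" applies, and 4.1 restricts the offer to those who "successfully complete Week 100 (without meeting study defined withdrawal criteria) will be given the option to continue". In the third, 5.5.5.2 says "the Investigator should confirm the definition is met by initiating a repeat of the HIV-1 RNA assessment", but 4.2.3 mentions one repeat and then the approval decision, without saying which comes first. A retest of exactly 50 c/mL is covered by neither the below-50 rule nor the above-50 rule. These are counts of combinations, not shares of participants.

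**The case against.** The best defence is that 5.5.5.3 made a deliberate choice. Waiting for resistance results lets the next regimen be selected on evidence, and Section 6.9.1 itself warns of resistance when long-acting dosing is interrupted and concentrations fall. The Medical Monitor also has to be consulted on dose interruptions (6.9) and on the choice of HAART (4.2.4). This has weight, and the cost to regimen choice is real. It does not settle the matter. The participant would be on HAART rather than uncovered, the regimen can be adjusted when results arrive, and the consultation on dose interruptions does not expressly cover giving a scheduled injection after CVF.

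A reader might infer several stronger points that the protocol does not support:

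- *That 5.5.5.3 is silent on injections after CVF.* It is not. It has a permissive rule, and through 6.1 that rule reaches the injectables. What is missing is a limit.
- *That the Medical Monitor may admit a CVF participant to the Extension.* Approval is an added condition, not a waiver. The general stopping wording bars entry, and 4.2.5 excludes waivers and exemptions.
- *That 6.2 contradicts 4.2.3.* Section 6.2 says who is offered the Extension but not that only they are. It is incomplete, and 4.2.3 is the operative text.
- *That 9 and 17 weeks are expected delays.* They are outer limits, conditional on a turnaround that is not given.

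**Conclusion.** The point holds as a minor one of participant safety and consistent conduct. As written, 5.5.5.3 permits an irreversible dose of a failing regimen after CVF. That fits poorly with the mandatory stop in the same section and with 2.3.1. Each further on-schedule injection moves the latest HAART start by 4 weeks on Q4W or 8 weeks on Q8W. This assumes that resistance results are still outstanding when the injection falls due and that the investigator uses the discretion given. The number of participants affected cannot be derived from the document.

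The Extension band and Section 6.2 need alignment only: CVF already bars entry, and the open case is a first value of 200 c/mL or more on retest. No effect on the primary endpoint, CVF counts or resistance sampling is claimed.

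**What to change.** **Main change, 5.5.5.3.** State that no further CAB LA or RPV LA injection is given once CVF is confirmed. State also that HAART starts within the existing 4.2.4 window, counted from the last injection given before confirmation, and is adjusted if needed when resistance results arrive. Using the existing window avoids creating a second deadline.

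**Alignment edits.** In 4.2.3 and 1.4.3, set the approvable retest band at 50 or more and below 200 c/mL. Say that a first value of 200 c/mL or more on retest is confirmed under 5.5.5.2 before any Extension decision. In 6.2, add the Medical Monitor approval route.

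**Cost.** Amendment wording in four sections and a memo to sites. No new assay or visit is needed, since 5.5.5.2 already asks for the confirmatory test. The clinical downside is that some follow-on regimens will be chosen before the resistance results are known.
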